Study Title: Radiographic Evaluation of Delayed Solid Organ Complications Multicenter Trial

Short Title: REDSOC

Principal Investigator: [name]

Co-Investigators: [name]; [name]

Principal Site: Penn Medicine Lancaster General Health

Key Roles and Study Governance:

[name]: Principal Investigator

[name]: Research Coordinator

[name]: Statistical Support

Protocol Date: 3/23/2021

Background & Significance

Non-operative management of splenic and hepatic injuries has become one of the standards of care in the management of hemodynamically stable patients. Institutional variance exists in management of these injuries regarding serial laboratory values, transfusion thresholds, the utility of interventional radiology/operative management, follow up imaging, and management of delayed findings on this imaging. The delayed complications found both clinically and with follow up imaging vary in the literature from nearly 0% to >15% of cases. There is no clear evidence as to the necessity of repeat imaging or frequency of intervention in blunt splenic and hepatic injuries. Some studies recommend only follow up

imaging for high grade injuries, whereas other studies have found no correlation between grade of injury and complications.

Our group approached this question through a dual institution, retrospective pilot study observing the management of delayed splenic and hepatic complications found on repeat imaging. This study was performed in the adult population and a current study is ongoing in the pediatric population. Imaging was obtained either via the institutions standard protocol (SP) or physician discretion (PD) (lab or vital sign abnormalities, clinical change, etc). There were 235 splenic injuries with 45% undergoing repeat imaging. 64% of these were due to PD. Complications were found in 47% of SP and 42% of PD patients (p=0.683). Interventions performed for these complications was done for 56% SP v. 21% of PD patients (p=0.027). This pilot study suggested that patients with blunt splenic injuries should undergo repeat imaging for delayed complications and that those who underwent repeat imaging by SP had complications identified sooner (2.4 v 4.4 days) and treated earlier than the PD group.

Of the 365 liver injuries, 33.4% underwent repeat imaging with a majority (59%) of these due to physician discretion. Complications were found in 20% of SP patients and 27% of PD patients (p=0.395). Interventions were performed in 20% SP v. 25% PD patients that had complications (p=1.00). In the liver injury group there was no difference found between complications or interventions performed when assessed by SP or PD; waiting to perform repeat imaging based on PD could prevent unnecessary imaging in blunt liver injuries.

In this small pilot study we were unable to achieve all of our primary and secondary endpoints. Additionally, interventions in low grade injuries are uncommon, and a larger data set would allow for delineation in management between low, moderate and high grade splenic and hepatic injuries. This study did not have power due to a limited number of patients receiving interventions, thus making characterization of types of interventions and final outcomes difficult.

A large multicenter trial would allow for appropriate power for the study and thus allow for us to meet our endpoints. There are multiple variables affecting the management of blunt splenic and hepatic injuries and currently no clear guidelines exist in regards to repeat imaging. Gaining a better understanding of types of delayed complications, how they present, and current management strategies would assist in creating a standardized algorithm in the treatment of this patient population.

Specific Aims of Multicenter Study

Aim 1: To define which blunt splenic and hepatic injuries are at risk of delayed complications in order to develop a societal management guideline.

Aim 2: To ascertain which patients warrant repeat imaging and when this imaging should be performed.

Aim 3: To define what interventions are needed based upon delayed complications found radiographically.

Aim 4: To analyze 30 day readmission rates to the hospital due to spleen and/or liver injury.

Methods

This will be a retrospective observational study. Patients will be managed according to the surgeon's discretion. The study will enroll a total of 5,000 subjects at minimum. This study plans to enroll 200 patients at our institution, Penn Medicine Lancaster General Health. The number of subjects that will be enrolled at each additional participating site is 200.

Inclusion Criteria:

• All patients (all ages) who present with blunt trauma to the spleen and/ or liver

Exclusion Criteria:

- Patients who suffer a penetrating mechanism
- Patients transferred out to another facility prior to admission

Updated Terms/Definitions:

 Clinical Change (CC) (to replace Physician Discretion)- repeat imaging prompted by patient factors including vital sign changes, lab abnormalities, abdominal pain, and patient symptoms Non Clinical Change (NCC) (to replace Standard Protocol)- repeat imaging prompted by institutional protocol/ recommendations, individual physician practice pattern, or that performed on a scheduled basis

The time frame for data query will be from IRB approval (2020) until December 31, 2023. The electronic medical record (EMR) may be used in order to identify participants who match study defined demographic criteria.

Primary Outcome: Delayed complications found on repeat imaging

Secondary Outcomes: Timing to repeat imaging/ intervention, interventions performed based on complications found, mortality, length of stay, blood transfusion requirements, VTE prophylaxis, and 30 day readmission variables [readmission within 30 days for spleen and/or liver injury, readmission CT scan, interventions performed].

Variables

List specific variables to be collected & analyzed: Age, sex, time from injury, Injury Severity Score (ISS), Abbreviated Injury Scale (AIS), Trauma and Injury Severity Score (TRISS), mechanism of injury, initial vital signs, anticoagulant use and reversal agents, initial and repeat imaging, grade of organs injured, complications found, details regarding initial and any delayed interventions, blood transfusions, details regarding venous thromboembolism prophylaxis, venous thromboembolism complications, hospital length of stay, intensive care unit length of stay, mortality, and 30 day readmission variables [readmission within 30 days for spleen and/or liver injury, readmission CT scan, interventions performed].

Data Collection and Statistical Analysis

Standardized data will be collected for each patient meeting inclusion criteria (see data collection tool). The de-identified data for each patient will be entered into a secure REDCap database. A total of 5,000 patients (3,500 splenic injuries and 1,500

hepatic injuries) is recommended to identify a significant difference between the non clinical change and clinical change group. Complications found on repeat imaging will be assessed using univariate and multivariate analysis.

Categorical variables will be compared using Fisher's exact test or Chi-squared test. Continuous variables will be assessed using Student's t-test. For multivariate analysis, a mixed effect multinomial logistic regression will be run with a binary outcome of whether the patient had a delayed complication. Another mixed effect multinomial logistic regression will be run with a binary outcome of whether the patient had an intervention performed. Additional analysis will be completed to determine if there is optimal timing for repeat imaging to identify complications. Data will be reported as adjusted odds ratios with 95% confidence intervals. Statistical significance will be defined by a p<0.05.

Sample Size and Power Estimates

A retrospective pilot study was completed with 235 patients with splenic injuries and 365 hepatic injuries. Of the patients with splenic injuries, 105 underwent repeat imaging, 46 had organ specific complications, and 16 had an intervention performed. Of the patients with hepatic injuries, 122 underwent repeat imaging, 30 had organ specific complications, and 12 had an intervention performed.

Spleen Power Analysis

Combined complication rate for patients who had repeat imaging: 46/105 = 0.44Standard protocol complication rate: 18/38 = 0.47Physician discretion complication rate: 28/67 = 0.42

Complication Rate:	Complication Rate:	Odds Ratio	Sample Size
Standard protocol	Physician discretion		(Total Population)
0.46	0.43	0.89	8,614
0.47	0.42	0.82	3,100
0.48	0.41	0.75	1,582

Liver Power Analysis

Combined complication rate for patients who had repeat imaging: 30/122 = 0.25Standard protocol complication rate: 10/50 = 0.20Physician discretion complication rate: 20/72 = 0.27

Complication Rate:	Complication Rate:	Odds Ratio	Sample Size
Standard protocol	Physician discretion		(Total Population)
0.21	0.26	1.32	2,256
0.20	0.27	1.48	1,150
0.19	0.28	1.66	696

Consent Procedures

This is a retrospective observational study in which data will be retrospectively recorded on patients according to institutional protocols. Data will be input into REDcap database without any patient identifiers. Thus, a waiver of consent is requested.

Confidentiality and Privacy

Participant confidentiality and privacy is strictly held in trust by the participating investigators, their staff, and the sponsor(s) and their interventions. This confidentiality is extended to cover the clinical information relating to participants. Therefore, the study protocol, documentation, data, and all other information generated will be held in strict confidence. No information concerning the study or the data will be released to any unauthorized third party without prior written approval of the sponsor.

All research activities will be conducted in as private a setting as possible.

Authorized representatives of the sponsor, representatives of the Institutional Review Board (IRB), regulatory agencies or pharmaceutical company supplying study product may inspect all documents and records required to be maintained by the investigator, including but not limited to, medical records (office, clinic, or hospital) and pharmacy records for the participants in this study. The clinical study site will permit access to such records.

The study participant's contact information will be securely stored at each clinical site for internal use during the study. At the end of the study, all records will continue to be kept in a secure location for 6 years as dictated by the HRPP.

Study participant research data, which is for purposes of statistical analysis and scientific reporting, will be transmitted to and stored at the on secure servers or in REDCap, a HIPAA compliant database management system. This will not include the participant's contact or identifying information. Rather, individual participants and their research data will be identified by a unique study identification number. The study data entry and study management systems used by clinical sites and by research staff will be secured and password protected. At the end of the study, all study databases will be de-identified and archived at Lancaster General Health Research Institute.

Risks and Adverse Event Reporting

The data collected and transferred to REDcap for the multicenter trial would be devoid of any patient identifiers and thus is a low risk study. The only risk to the subject is a confidentiality breach associated with their data being accessed and included as part of this retrospective chart review. However, this study only contained de-identified data entered into the REDCap. If an adverse event occurs, once investigators have learned of this, the IRB will be notified within 48 hours.

Potential Benefits

The benefit would be to improve clinical practice as the incidence and characterization of delayed complications in blunt solid organ injury is not well understood. Additionally, understanding types of delayed complications, when they are identified, and if/ how they are treated will allow for more definitive guidelines and improved outcomes for this population of patients.

Risk/ Benefit Analysis

This study is no more than minimal risk since it is a retrospective observational study that does not contain any patient identifiers

Waiver of Consent and HIPAA

We are seeking a waiver of consent and HIPAA authorization for this study.

Waiver or alteration of required elements of consent: According to HHS CFR 45.46.116(d): An IRB may approve a consent procedure which does not include, or which alters, some or all of the elements of informed consent, or waive the requirements to obtain informed consent. This study qualifies for a waiver of informed consent due to each of the following:

- This study is no more than minimal risk to subjects: there is no intervention or interaction with subjects, it is observational in nature and will only involve medical chart review.
- The waiver or alteration would not adversely affect the rights and welfare of the subjects: rights and welfare of the subjects will not be adversely impacted

as this study is similar to many other retrospective observational studies. No subjects will be identified individually.

- The research could not practicably be carried out without the waiver or alteration: the attempt to contact subjects poses a greater risk than this study. It would be impractical to contact subjects as data collection occurs retrospectively, well after the patient is discharged from the hospital, and to contact subjects, would require patient identifiers, which are not provided by the data sources.
- Where appropriate, subjects will be provided with additional: there are no plans to contact subjects as it is not necessary to the analysis of this study.

For the waiver of HIPAA:

• This study poses no more than minimal risk to privacy: will protect identifiers from improper use and disclosure; will de-identify data prior to sharing with other institutions. Each of the study sites is assigned a site identifier to maintain privacy. Please note that each study site can only access data pertaining to their site alone on REDCap. However, only the lead site (Penn Medicine LGH) principal investigator ([name]) has the ability to link specific study institutions with their data.

Conflict of Interest Policy

All Investigators will follow the Penn Medicine Lancaster General Health Policy on Conflicts of Interest Related to Research.

The independence of this study from any actual or perceived influence, such as by the pharmaceutical industry, is critical. Therefore, any actual conflict of interest of persons who have a role in the design, conduct, analysis, publication, or any aspect of this trial will be disclosed and managed. Furthermore, persons who have a perceived conflict of interest will be required to have such conflicts managed in a way that is appropriate to their participation in the design and conduct of this trial.

Publication Plan

After completion of the study and analysis and interpretation of the data, a manuscript for publication will be written with the principal investigator as the lead author. The sub-investigators will be listed in order of effort dedicated to the study. The manuscript will be targeted for publication in trauma or critical care journal.

References

- 4. Østerballe L, Helgstrand F, Axelsen T, et al. Hepatic pseudoaneurysm after traumatic liver injury; is CT follow- up warranted? *J Trauma Manag Outcomes.* 2014; 8:18.

Non-operative management of splenic and hepatic injuries has become one of the standards of care in the management of hemodynamically stable patients. Institutional variance exists in management of these injuries regarding serial laboratory values, transfusion thresholds, the utility of interventional radiology/operative management, follow up imaging, and management of delayed findings on this imaging. The delayed complications found both clinically and with follow up imaging vary in the literature from nearly 0% to >15% of cases. There is no clear evidence as to the necessity of repeat imaging or frequency of intervention in blunt splenic and hepatic injuries. Some studies recommend only follow up

imaging for high grade injuries, whereas other studies have found no correlation between grade of injury and complications.

Our group approached this question through a dual institution, retrospective pilot study observing the management of delayed splenic and hepatic complications found on repeat imaging. This study was performed in the adult population and a current study is ongoing in the pediatric population. Imaging was obtained either via the institutions standard protocol (SP) or physician discretion (PD) (lab or vital sign abnormalities, clinical change, etc). There were 235 splenic injuries with 45% undergoing repeat imaging. 64% of these were due to PD. Complications were found in 47% of SP and 42% of PD patients (p=0.683). Interventions performed for these complications was done for 56% SP v. 21% of PD patients (p=0.027). This pilot study suggested that patients with blunt splenic injuries should undergo repeat imaging for delayed complications and that those who underwent repeat imaging by SP had complications identified sooner (2.4 v 4.4 days) and treated earlier than the PD group.

Of the 365 liver injuries, 33.4% underwent repeat imaging with a majority (59%) of these due to physician discretion. Complications were found in 20% of SP patients and 27% of PD patients (p=0.395). Interventions were performed in 20% SP v. 25% PD patients that had complications (p=1.00). In the liver injury group there was no difference found between complications or interventions performed when assessed by SP or PD; waiting to perform repeat imaging based on PD could prevent unnecessary imaging in blunt liver injuries.

In this small pilot study we were unable to achieve all of our primary and secondary endpoints. Additionally, interventions in low grade injuries are uncommon, and a larger data set would allow for delineation in management between low, moderate and high grade splenic and hepatic injuries. This study did not have power due to a limited number of patients receiving interventions, thus making characterization of types of interventions and final outcomes difficult.

A large multicenter trial would allow for appropriate power for the study and thus allow for us to meet our endpoints. There are multiple variables affecting the management of blunt splenic and hepatic injuries and currently no clear guidelines exist in regards to repeat imaging. Gaining a better understanding of types of delayed complications, how they present, and current management strategies would assist in creating a standardized algorithm in the treatment of this patient population.

Specific Aims of Multicenter Study

Aim 1: To define which blunt splenic and hepatic injuries are at risk of delayed complications in order to develop a societal management guideline.

Aim 2: To ascertain which patients warrant repeat imaging and when this imaging should be performed.

Aim 3: To define what interventions are needed based upon delayed complications found radiographically.

Aim 4: To analyze 30 day readmission rates to the hospital due to spleen and/or liver injury.

Methods

This will be a retrospective observational study. Patients will be managed according to the surgeon's discretion. The study will enroll a total of 5,000 subjects at minimum. This study plans to enroll 200 patients at our institution, Penn Medicine Lancaster General Health. The number of subjects that will be enrolled at each additional participating site is 200.

Inclusion Criteria:

• All patients (all ages) who present with blunt trauma to the spleen and/ or liver

Exclusion Criteria:

- Patients who suffer a penetrating mechanism
- Patients transferred out to another facility prior to admission

Updated Terms/Definitions:

• **Clinical Change (CC) (to replace Physician Discretion)**- repeat imaging prompted by patient factors including vital sign changes, lab abnormalities, abdominal pain, and patient symptoms

• Non Clinical Change (NCC) (to replace Standard Protocol)- repeat imaging prompted by institutional protocol/ recommendations, individual physician practice pattern, or that performed on a scheduled basis

The time frame for data query will be from IRB approval (2020) until December 31, 2023. The electronic medical record (EMR) may be used in order to identify participants who match study defined demographic criteria.

Primary Outcome: Delayed complications found on repeat imaging

Secondary Outcomes: Timing to repeat imaging/ intervention, interventions performed based on complications found, mortality, length of stay, blood transfusion requirements, VTE prophylaxis, and 30 day readmission variables [readmission within 30 days for spleen and/or liver injury, readmission CT scan, interventions performed].

Variables

List specific variables to be collected & analyzed: Age, sex, time from injury, Injury Severity Score (ISS), Abbreviated Injury Scale (AIS), Trauma and Injury Severity Score (TRISS), mechanism of injury, initial vital signs, anticoagulant use and reversal agents, initial and repeat imaging, grade of organs injured, complications found, details regarding initial and any delayed interventions, blood transfusions, details regarding venous thromboembolism prophylaxis, venous thromboembolism complications, hospital length of stay, intensive care unit length of stay, mortality, and 30 day readmission variables [readmission within 30 days for spleen and/or liver injury, readmission CT scan, interventions performed].

Data Collection and Statistical Analysis

Standardized data will be collected for each patient meeting inclusion criteria (see data collection tool). The de-identified data for each patient will be entered into a secure REDCap database. A total of 5,000 patients (3,500 splenic injuries and 1,500

hepatic injuries) is recommended to identify a significant difference between the non clinical change and clinical change group. Complications found on repeat imaging will be assessed using univariate and multivariate analysis.

Categorical variables will be compared using Fisher's exact test or Chi-squared test. Continuous variables will be assessed using Student's t-test. For multivariate analysis, a mixed effect multinomial logistic regression will be run with a binary outcome of whether the patient had a delayed complication. Another mixed effect multinomial logistic regression will be run with a binary outcome of whether the patient had an intervention performed. Additional analysis will be completed to determine if there is optimal timing for repeat imaging to identify complications. Data will be reported as adjusted odds ratios with 95% confidence intervals. Statistical significance will be defined by a p<0.05.

Sample Size and Power Estimates

A retrospective pilot study was completed with 235 patients with splenic injuries and 365 hepatic injuries. Of the patients with splenic injuries, 105 underwent repeat imaging, 46 had organ specific complications, and 16 had an intervention performed. Of the patients with hepatic injuries, 122 underwent repeat imaging, 30 had organ specific complications, and 12 had an intervention performed.

Spleen Power Analysis

Combined complication rate for patients who had repeat imaging: 46/105 = 0.44Standard protocol complication rate: 18/38 = 0.47Physician discretion complication rate: 28/67 = 0.42

Complication Rate:	Complication Rate:	Odds Ratio	Sample Size
Standard protocol	Physician discretion		(Total Population)
0.46	0.43	0.89	8,614
0.47	0.42	0.82	3,100
0.48	0.41	0.75	1,582

Liver Power Analysis

Combined complication rate for patients who had repeat imaging: 30/122 = 0.25Standard protocol complication rate: 10/50 = 0.20Physician discretion complication rate: 20/72 = 0.27

Complication Rate: Standard protocol	Complication Rate: Physician discretion	Odds Ratio	Sample Size (Total Population)
0.21	0.26	1.32	2,256
0.20	0.27	1.48	1,150
0.19	0.28	1.66	696

Consent Procedures

This is a retrospective observational study in which data will be retrospectively recorded on patients according to institutional protocols. Data will be input into REDcap database without any patient identifiers. Thus, a waiver of consent is requested.

Confidentiality and Privacy

Participant confidentiality and privacy is strictly held in trust by the participating investigators, their staff, and the sponsor(s) and their interventions. This confidentiality is extended to cover the clinical information relating to participants. Therefore, the study protocol, documentation, data, and all other information generated will be held in strict confidence. No information concerning the study or the data will be released to any unauthorized third party without prior written approval of the sponsor.

All research activities will be conducted in as private a setting as possible.

Authorized representatives of the sponsor, representatives of the Institutional Review Board (IRB), regulatory agencies or pharmaceutical company supplying study product may inspect all documents and records required to be maintained by the investigator, including but not limited to, medical records (office, clinic, or hospital) and pharmacy records for the participants in this study. The clinical study site will permit access to such records.

The study participant's contact information will be securely stored at each clinical site for internal use during the study. At the end of the study, all records will continue to be kept in a secure location for 6 years as dictated by the HRPP.

Study participant research data, which is for purposes of statistical analysis and scientific reporting, will be transmitted to and stored at the on secure servers or in REDCap, a HIPAA compliant database management system. This will not include the participant's contact or identifying information. Rather, individual participants and their research data will be identified by a unique study identification number. The study data entry and study management systems used by clinical sites and by research staff will be secured and password protected. At the end of the study, all study databases will be de-identified and archived at Lancaster General Health Research Institute.

Risks and Adverse Event Reporting

The data collected and transferred to REDcap for the multicenter trial would be devoid of any patient identifiers and thus is a low risk study. The only risk to the subject is a confidentiality breach associated with their data being accessed and included as part of this retrospective chart review. However, this study only contained de-identified data entered into the REDCap. If an adverse event occurs, once investigators have learned of this, the IRB will be notified within 48 hours.

Potential Benefits

The benefit would be to improve clinical practice as the incidence and characterization of delayed complications in blunt solid organ injury is not well understood. Additionally, understanding types of delayed complications, when they are identified, and if/ how they are treated will allow for more definitive guidelines and improved outcomes for this population of patients.

Risk/ Benefit Analysis

This study is no more than minimal risk since it is a retrospective observational study that does not contain any patient identifiers

Waiver of Consent and HIPAA

We are seeking a waiver of consent and HIPAA authorization for this study.

Waiver or alteration of required elements of consent: According to HHS CFR 45.46.116(d): An IRB may approve a consent procedure which does not include, or which alters, some or all of the elements of informed consent, or waive the requirements to obtain informed consent. This study qualifies for a waiver of informed consent due to each of the following:

- This study is no more than minimal risk to subjects: there is no intervention or interaction with subjects, it is observational in nature and will only involve medical chart review.
- The waiver or alteration would not adversely affect the rights and welfare of the subjects: rights and welfare of the subjects will not be adversely impacted

as this study is similar to many other retrospective observational studies. No subjects will be identified individually.

- The research could not practicably be carried out without the waiver or alteration: the attempt to contact subjects poses a greater risk than this study. It would be impractical to contact subjects as data collection occurs retrospectively, well after the patient is discharged from the hospital, and to contact subjects, would require patient identifiers, which are not provided by the data sources.
- Where appropriate, subjects will be provided with additional: there are no plans to contact subjects as it is not necessary to the analysis of this study.

For the waiver of HIPAA:

• This study poses no more than minimal risk to privacy: will protect identifiers from improper use and disclosure; will de-identify data prior to sharing with other institutions. Each of the study sites is assigned a site identifier to maintain privacy. Please note that each study site can only access data pertaining to their site alone on REDCap. However, only the lead site (Penn Medicine LGH) principal investigator ([name]) has the ability to link specific study institutions with their data.

Conflict of Interest Policy

All Investigators will follow the Penn Medicine Lancaster General Health Policy on Conflicts of Interest Related to Research.

The independence of this study from any actual or perceived influence, such as by the pharmaceutical industry, is critical. Therefore, any actual conflict of interest of persons who have a role in the design, conduct, analysis, publication, or any aspect of this trial will be disclosed and managed. Furthermore, persons who have a perceived conflict of interest will be required to have such conflicts managed in a way that is appropriate to their participation in the design and conduct of this trial.

Publication Plan

After completion of the study and analysis and interpretation of the data, a manuscript for publication will be written with the principal investigator as the lead author. The sub-investigators will be listed in order of effort dedicated to the study. The manuscript will be targeted for publication in trauma or critical care journal.

References

- 4. Østerballe L, Helgstrand F, Axelsen T, et al. Hepatic pseudoaneurysm after traumatic liver injury; is CT follow- up warranted? *J Trauma Manag Outcomes.* 2014; 8:18.

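### The power table counts re-imaged patients but the 3,500/1,500 targets count all injured patients, so at the pilot's re-imaging shares power for the central rows is roughly 45–60%, not the 80% behind the table

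*Supplement*

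**What the plan says.** Under Data Collection and Statistical Analysis, the protocol gives the target as "A total of 5,000 patients (3,500 splenic injuries and 1,500" for liver, and presents this as the size needed to show that NCC and CC differ. Eligibility covers every blunt spleen or liver injury at any age and does not require repeat imaging. NCC and CC are defined by the reason for a repeat image, so a patient without one belongs to neither group. The primary outcome is a delayed complication seen on repeat imaging.

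Under Sample Size and Power Estimates, the pilot is described: "A retrospective pilot study was completed with 235 patients with splenic injuries and 365 hepatic injuries". For spleen, "Of the patients with splenic injuries, 105 underwent repeat imaging, 46 had organ specific complications, and 16 had an intervention performed"; for liver, 122 of 365 were re-imaged and 30 had complications. The planning rates are taken among the re-imaged: "Combined complication rate for patients who had repeat imaging: 46/105" for spleen overall, with 18/38 against 28/67 by reason for imaging. For liver they are 30/122 overall, with 10/50 against 20/72. Each organ has three rows of assumed rates, and the result column is headed "Sample Size (Total Population"). The central rows give 3,100 (0.47 v 0.42) and 1,150 (0.20 v 0.27).

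The only error-rate statement is "Statistical significance will be defined by a p<0.05". No power, sidedness or allocation ratio is given. The background says "A large multicenter trial would allow for appropriate power for the study".

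**The concern.** The targets lie a little above the central rows, by 13% for spleen (3,500/3,100) and 30% for liver (1,500/1,150), as if table and target counted the same patients. They do not. A patient who is never re-imaged adds to the 3,500 or the 1,500 but contributes nothing to the NCC–CC comparison. In the pilot, more than half of the splenic and two thirds of the hepatic patients were in that position.

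The study is meant to feed a management guideline. The pilot report already read non-significant liver comparisons as showing no difference, and suggested that waiting for a clinical prompt might spare imaging. If the multicentre comparison has about even odds of detecting the planned difference while being described as adequately powered, a non-significant result could be given the same reading with more authority than it deserves.

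**Working it through.** **Inputs.** Rates, group sizes and re-imaging counts come from Sample Size and Power Estimates, and the targets from Data Collection and Statistical Analysis. Alpha is 0.05. Two-sided testing, 80% power and 1:1 allocation are inferred, because together they reproduce the table.

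**Step 1: reproduce the table.** Pooled two-proportion formula without continuity correction, per group:

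n = [1.960·√(2p̄(1−p̄)) + 0.842·√(p₁(1−p₁) + p₂(1−p₂))]² / (p₁ − p₂)²

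- Spleen, 0.47 v 0.42: (1.3775 + 0.5908)² / 0.05² = 1,549.6, rounded up to 1,550 per group; total 3,100. Table: 3,100.
- Liver, 0.20 v 0.27: (1.1752 + 0.5029)² / 0.07² = 574.8, rounded up to 575 per group; total 1,150. Table: 1,150.

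The other four rows (8,614; 1,582; 2,256; 696) also reproduce exactly. With 90% power, a one-sided test or the pilot's group sizes, the rows do not reproduce exactly. The totals are therefore both groups combined, in patients to whom those rates apply, that is, re-imaged patients.

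**Step 2: share that must be re-imaged.** Spleen 3,100/3,500 = 89%; liver 1,150/1,500 = 77%. Pilot shares: 105/235 = 44.7% and 122/365 = 33.4%.

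**Step 3: expected re-imaged patients.** Spleen 3,500 × 105/235 = 1,564; liver 1,500 × 122/365 = 501.

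**Step 4: power at those numbers.** Power = Φ{[|p₁ − p₂|·√n − 1.960·√(2p̄(1−p̄))] / √(p₁(1−p₁) + p₂(1−p₂))}, with n per group.

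- Spleen, 1:1, n = 781.9: (1.3981 − 1.3775)/0.7019 = 0.029; power 51%.
- Liver, 1:1, n = 250.7: (1.1083 − 1.1752)/0.5976 = −0.112; power 46%.

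The same calculation under other choices, at the pilot re-imaging shares:

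| Rates and allocation | Spleen | Liver |
|---|---|---|
| Central row, 1:1 | 51% | 46% |
| Central row, pilot split (38:67; 50:72) | 48% | 44% |
| Unrounded pilot rates, 1:1 | 60% | 53% |
| Unrounded pilot rates, pilot split | 57% | 51% |
| Largest-difference row (0.48 v 0.41; 0.19 v 0.28), 1:1 | 80% | 66% |

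**Step 5: sensitivity to the re-imaging share** (central rows, 1:1):

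| Share re-imaged | Spleen | Liver |
|---|---|---|
| 30% | 37% | 42% |
| 60% | 64% | 70% |
| 90% | 81% | 86% |
| 100% | 85% | 89% |

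**Step 6: detectable difference.** With 1,564 and 501 re-imaged at the pilot split, and the standard-protocol rate held at 0.47 or 0.20, 80% power is reached at about 7.3 points (spleen) and 11.1 points (liver). The central rows assume 5 and 7.

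**Minor note.** 20/72 is 0.278, not 0.27. At 0.20 v 0.278 the liver row needs about 942 re-imaged patients rather than 1,150, so this slip is on the cautious side.

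**The case against.** The strongest reply is that no single power figure follows from the documents, and that is right. The re-imaging share comes from an adult, two-institution pilot, while this study takes all ages at many sites, so practice may differ. The pilot's group split may not carry over either: NCC now includes imaging driven by an individual physician's practice pattern, which the earlier discretion label could have covered. A reader might infer that the plan delivers exactly 48% and 44%. Those values combine the unit mismatch with the pilot split and the rounded rates; the mismatch alone, on the table's own 1:1 basis, gives 51% and 46%.

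The table is also a grid. For the larger spleen difference, 0.48 v 0.41, the expected 1,564 nearly meets the tabulated 1,582. The plan does not name the central rows as its basis, though the targets sit just above them. In addition, 5,000 is stated as a minimum, and the column label may mean only that both groups are combined.

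A reader might further infer that the 3,500:1,500 split is wrong because the pilot had 235 splenic and 365 hepatic injuries. The documents do not support this. Nothing ties the target to the pilot's organ mix, and patients may have both injuries in an overlap that is not given. Nor is interval reporting missing: adjusted odds ratios with 95% confidence intervals are already planned.

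None of this removes the mismatch. The table needs re-imaged patients, the target counts injured patients, and no step links the two.

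**Conclusion.** The point stands as a mismatch of units in the study's only sample-size justification. At the pilot's re-imaging shares, the stated targets give roughly 45–60% power for the central rows (44% at the lowest combination, 60% at the highest). They reach about 80% for spleen only in the larger-difference row at 1:1, and in no tabulated row for liver.

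This rests on three assumptions: the pilot re-imaging shares, 80% power and two-sided testing as the table's unstated basis, and simple two-group comparisons. Site clustering and covariate adjustment are outside these figures. A much higher re-imaging share, near 90% for spleen and somewhat under 80% for liver, would remove the shortfall, but nothing in the documents leads one to expect it.

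**What to change.** - Label the table column as re-imaged patients, both groups combined at 1:1, and state the power and sidedness.
- Give the expected number of re-imaged patients per organ from 3,500 and 1,500 (about 1,564 and 501 at the pilot shares). Beside it give either the resulting power for the central rows, with its range by re-imaging share, or the difference detectable with 80% power (about 7.3 and 11.1 points at the pilot split).
- Track accrual by re-imaged patients per organ rather than by injuries alone.
- State that a non-significant NCC–CC comparison will not be read as showing no difference, and rest the interpretation on the confidence interval already planned.
- If 20/72 is corrected to 0.278, recompute both the liver row (about 942) and the liver power on that same rate, so that the two are not mixed.

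The cost is protocol wording and a less favourable power statement. No added patients are needed.
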